#### Lens Fit Success

Lens fit success was converted to a binary response as  $Y = 1$  if lens optimization was achieved in 4 lenses or less and  $Y = 0$  otherwise for analysis purposes. From the historical data there was 100% rate for lens fit success there for a worst-case scenario of 98% was used as the reference rate. Assuming a correlation of 0.70 between left and right eyes within the same subject, a total of 2000 replicating trials were simulated. Given the rare event binary outcome,  $Y=0$  each replicated sample was analyzed using a Bayesian beta-binomial model with correlated binary data (Diniza et al; 2010). For each simulated trial, the lower bound of the 99% central posterior credible interval constructed for the percentage successful lens fit for the Test lens was compared to a margin of 90%. With the proposed sample size, there was at least 80% of the estimated 99% credible intervals with the lower bound being above 90%.

Table 8 displays the sample size estimates and associated power by endpoints. As indicated below, co-primary safety endpoints were powered ~92% individually yielding a combined power of ~84%. With respect to co-primary efficacy each hypothesis was powered to ~99% power provided a combine power of ~95%. Therefore, the overall combined study power for co-primary safety and co-primary efficacy hypotheses is ~79% and is considered reasonable to support any conclusions from these analyses. Furthermore, secondary endpoints were powered to achieve at least 80% statistical power. This was considered to have a minimal impact on overall study power because of the multibranch gate keeping approach being implemented.

Table 8: Sample Size Estimates by Endpoint

Endpoint Type	Endpoint	Test Type	Sample Size	Power (%)
Primary Efficacy	VP - Distance	Superiority (0.00)	17	99.4
	VP - Intermediate	Superiority (0.17)	11	99.3
	VP - Near	Superiority (0.17)	48	99.0
	CLUE Vision-Hyperopes	Superiority (36)	14	99.4
	CLUE Vision Myopes	Superiority (41)	18	99.0

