### Primary Efficacy Endpoint Sample Size Calculations:

# Clinical Study Protocol

## Johnson & Johnson Vision Care, Inc.

### Binocular HLHC Visual Performance and CLUE Vision Scores

Sample size calculations for each co-primary efficacy endpoint were carried separately out using a 2-sided one sample mean t-test, with a two-sided type I rate of 1%. The calculation was performed using the POWER procedure in SAS Version 9.4.

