# Clinical Study Protocol

## Johnson & Johnson Vision Care, Inc.

Endpoint Type	Endpoint	Test Type	Sample Size	Power (%)
Primary Safety	Grade 3 + SLF	Statistically less than (5%)	100	92.6
	Unacceptable Lens fitting	Statistically less than (5%)	100	92.6
Secondary	CLUE Vision-Hyperopes	Superiority (41)	16	82.4
	CLUE Vision Myopes	Superiority (46)	15	82.3
	CLUE Comfort (Hyperopes + Myopes)	Superiority (52)	11	83.8
	CLUE Handling (Hyperopes + Myopes)	Superiority (53)	17	83.7
	Lens Fit Success	Superiority (90%)	92	82.1

Based on the table above a total of at least 100 subjects a required to complete the study. To account for screen failures and subject dropout Up to 120 subjects (72 myopes and 48 hyperopes) will be enrolled to ensure at least 100 (60 myopes and 40 hyperopes) complete the study.

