### 14.4. Level of Statistical Significance

All *co-primary safety*, *co-primary efficacy* and *secondary* hypotheses will be tested using a multibranch gate keeping strategy. Study hypotheses will be evaluated sequentially as follows: First, co-primary safety hypotheses will be tested using 95% central posterior credible intervals for the probability of Grade or higher and unacceptable lens fitting. Both hypotheses must be met in order to test co-primary efficacy hypotheses. Since both hypotheses must pass to continue testing primary hypotheses, an overall family-wise type I error rate of 5% will be allocated to co-primary efficacy hypotheses using a Bonferroni approach. Each co-primary efficacy hypothesis will be tested using two-sided type I error rate of 1% (5 hypotheses total

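### The ~95% combined efficacy power, and the ~79% study power built on it, mix tests at different sample sizes and are not the power at the planned 100 completers

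*Combined protocol and SAP*

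**What the plan says.** Everything is in section 14.2 of the protocol unless noted.

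- The text above Table 8 states that for co-primary efficacy "each hypothesis was powered to ~99% power provided a combine power of ~95" percent. It gives about 92% for each safety test and about 84% for the pair, and concludes that "the overall combined study power for co-primary safety and co-primary efficacy hypotheses is ~79" percent, which it regards as adequate to support the study's conclusions.
- Table 8 gives the efficacy powers at endpoint-specific sizes: distance "Superiority (0.00) 17 99.4", intermediate "Superiority (0.17) 11 99.3", near "Superiority (0.17) 48 99.0", CLUE Vision in hyperopes n = 14 (99.4%) and in myopes n = 18 (99.0%). Both safety rows are at n = 100 (92.6%).
- The text below Table 8 reads "Based on the table above a total of at least 100 subjects a required to complete the study", made up of 60 myopes and 40 hyperopes.
- The efficacy calculations are one-sample t-tests "with a two-sided type I rate of 1" percent. Section 14.4 agrees: "Each co-primary efficacy hypothesis will be tested using two-sided type I error rate of 1" percent.
- Section 14.5 analyses CLUE Vision separately in each refractive group and visual acuity in the two groups combined. The planned efficacy tests therefore run at about 60, 40 and 100 subjects.

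**The concern.** A joint power figure should describe one trial. Here the efficacy factor is taken at 11 to 48 subjects and the safety factor at 100, and the product is presented as the power of the study. None of the five efficacy tests will be run at its Table 8 size.

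The sponsor relies on the 79%. As written, a reader learns that requiring all five efficacy tests to succeed costs about 5 points of power. If that cost almost disappears at the planned size, the planning risk sits with the two safety tests, and it is their assumptions (2% true event rate, 0.70 correlation between eyes) that deserve scrutiny.

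**Working it through.** **1. Reproduce the plan's figures.**
- Efficacy: 0.99^5 = 0.951. With the Table 8 entries, 0.994 × 0.993 × 0.990 × 0.994 × 0.990 = 0.962. Either matches about 95%.
- Overall: 0.84 × 0.95 = 0.798, matching about 79%.

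So the 95% is the product of powers at the Table 8 sizes, and the 79% is that product times the safety power at n = 100.

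**2. Efficacy power at the planned completers.** Inputs are the Table 7 means and SDs, the thresholds in section 2.3 and two-sided alpha 0.01. The noncentrality is δ = (|mean − threshold| / SD) × √n, and power is the probability that a noncentral t with n − 1 degrees of freedom and noncentrality δ exceeds t(0.995, n − 1). The opposite tail is negligible.

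| Endpoint | Difference / SD | n | δ | Critical t | Power |
|---|---|---|---|---|---|
| Distance acuity | 0.109 / 0.0848 = 1.285 | 100 | 12.85 | 2.626 | >99.99% |
| Intermediate acuity | 0.194 / 0.1129 = 1.718 | 100 | 17.18 | 2.626 | >99.99% |
| Near acuity | 0.085 / 0.1264 = 0.672 | 100 | 6.72 | 2.626 | 99.997% |
| CLUE Vision, hyperopes | 21.1 / 17.27 = 1.222 | 40 | 7.73 | 2.708 | 99.9999% |
| CLUE Vision, myopes | 19.6 / 16.84 = 1.164 | 60 | 9.02 | 2.662 | >99.9999% |

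The product is 99.997%. The five type II errors sum to about 2.8 × 10⁻⁵, so joint power is at least 99.997% whatever the correlation between endpoints. At 85% of the planned completers (85/51/34) it is still about 99.98%.

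**3. Overall figure at one set of sizes.**
- Keeping the plan's rounded safety pair: 0.84 × 0.99997 ≈ 84%.
- Using 92.6% for each safety test: 0.926² × 0.99997 = 85.7%.

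Correcting the efficacy factor alone moves 79.8% to 84%, a shift of 4 to 5 points. The remaining 2 points or so come from the plan's rounding of 92.6% down to 92% and the pair to 84%. Without independence, two safety tests at 92.6% each have joint power between 2 × 0.926 − 1 = 85.2% and 92.6%.

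**4. Sensitivity to the Table 7 effects.** At 100/60/40, two-sided 1%, endpoints taken as independent:

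| True effects as a share of Table 7 | Joint efficacy power |
|---|---|
| 100% | 99.997% |
| 75% | about 99% |
| 60% | about 89% (near about 92%, hyperopes about 97%) |
| 50% | about 64% |

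**5. The safety input.** The 92.6% was not reproduced. A grid simulation of the mixture model in section 14.5 (n = 100, eye correlation 0.70, intercept-only with a diffuse logit prior, upper limit of the central 95% interval below 5%) gave about 55% power at a true rate of 2%, 84% at 1% and 95% at 0.5%. This rests on one reading of the model, so it is a reason to recheck the input and not a replacement for it.

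**The case against.** The strongest reply is that the error is conservative and changes no decision. Efficacy power is higher than stated, the 100 completers come from the safety rows, and no hypothesis, alpha, population or decision rule is affected. That stands, and it limits the point to correcting a stated figure.

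The plan is also open about its inputs. Table 8 prints n beside every power, safety and efficacy are reported separately before being multiplied, and section 14.2 describes 99% as the minimum power for the efficacy endpoints. It would be unfair to say the mismatch is concealed. But the minimum is set endpoint by endpoint and is not carried into the 95% or the 79%, neither of which is given as a lower bound.

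A third reply is that 99.997% is itself conditional. Table 7 summarises per-protocol, first-period data, whereas section 14.5 tests the intent-to-treat population with a bootstrap. This also stands, and is why the replacement figure must carry its assumptions. The 95% intervals in the section 14.5 decision rules would only raise power above the 1% figures used here.

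A reader might infer that 79% falls short and more subjects are needed, or that true study power is 86%. The documents support neither. The shortfall from efficacy is a product of mismatched sizes, and 86% depends on a safety input that has not been verified.

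**Conclusion.** The point holds as a correction to the stated power. The 95% and the 79% are not the power of the planned trial. Under the Table 7 means and SDs and a two-sided 1% t-test, joint efficacy power at 100/60/40 is above 99.9%. Overall power is then essentially the joint safety power, about 84% to 86%, provided the plan's 92% to 92.6% per safety test is correct and the two tests are independent.

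A reader might go further and conclude that study power depends on the safety tests alone. That is true only near the Table 7 effects; at 60% of them efficacy would cost about 11 points.

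Whether each Table 8 efficacy power is right at its own n is a separate question. At the stated alpha they recompute to 98.4%, 98.3%, 97.2%, 91.8% and 96.9% in table order, a product of 83.6%. The mismatch of sample sizes would remain even if every entry were exact.

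**What to change.** In section 14.2:

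1. Replace the 95% with joint efficacy power at 100 completers (60 myopes, 40 hyperopes), stated as conditional on the Table 7 effects and accompanied by a sensitivity value such as about 89% at 60% of those effects.
2. Recheck the 92.6% safety power, then recompute the overall figure at that single set of sizes, stating the independence assumption. Do not print a higher overall figure before the recheck.
3. State that under the planning assumptions the two safety tests determine overall power.
4. Label the Table 8 efficacy sizes as per-endpoint sample size estimates, not trial power. Avoid calling them the smallest sizes giving 99%, since they do not reach it at the stated alpha.

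The cost is wording in the protocol and SAP plus one rerun of the safety simulation. Correcting the efficacy factor requires no change to enrolment.

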# Clinical Study Protocol

## Johnson & Johnson Vision Care, Inc.

Endpoint Type	Endpoint	Test Type	Sample Size	Power (%)
Primary Safety	Grade 3 + SLF	Statistically less than (5%)	100	92.6
	Unacceptable Lens fitting	Statistically less than (5%)	100	92.6
Secondary	CLUE Vision-Hyperopes	Superiority (41)	16	82.4
	CLUE Vision Myopes	Superiority (46)	15	82.3
	CLUE Comfort (Hyperopes + Myopes)	Superiority (52)	11	83.8
	CLUE Handling (Hyperopes + Myopes)	Superiority (53)	17	83.7
	Lens Fit Success	Superiority (90%)	92	82.1

Based on the table above a total of at least 100 subjects a required to complete the study. To account for screen failures and subject dropout Up to 120 subjects (72 myopes and 48 hyperopes) will be enrolled to ensure at least 100 (60 myopes and 40 hyperopes) complete the study.

### 14.3. Analysis Populations

#### **Safety Population:**

All subjects who were administered any test article excluding subjects who drop out prior to administering any test article. At least one observation should be recorded.

#### **Per-Protocol Population:**

All subjects who have successfully completed all visits and did not substantially deviate from the protocol as determined by the trial cohort review committee prior to database hard lock (Per-Protocol Population). Justification of excluding subjects with protocol deviations in the per-protocol population set will be documented in a memo to file.

#### **Intent-to-Treat (ITT) Population:**

All randomized subjects regardless of actual treatment and subsequent withdrawal from study or deviation from protocol. At least one observation should be recorded.

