# Clinical Study Protocol

## Johnson & Johnson Vision Care, Inc.

### 5. TEST ARTICLE ALLOCATION AND MASKING

#### 5.1. Test Article Allocation

The study lenses will be worn in a bilateral fashion using a single-arm design. Due to the nature of the design no randomization is required.

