**Clinical Study Protocol**  
**Johnson & Johnson Vision Care, Inc.**

Visit Information	Visit 1 Screening, Baseline, Treatment 1	Visit 2 Treatment 1 Follow-up 1 Optimization	Visit 3 Treatment 1 Follow-up 2
Time Point	Day 0	Day 3±1 from V1	Day 7±1 from V2
Estimated Visit Duration	2.5 hours	1.0 hour	1.5 hours
Baseline Inclusion/ Exclusion Criteria	x		
Continuance		x	x
Lens Selection	x	x (if modified)	x
Lens Insertion	x	x	x
10-Minute Settling	x	x (if modified)	
Visual Satisfaction / Subjective Acceptance	x	x	x
Study Lens Distance and Near Visual Acuity	x	x	x
Distance Over Refraction and Visual Acuity	x	x	x
Subjective Lens Fit Assessment	x	x	x
Binocular Over Refraction			x
Compliance		x	x
Follow-up PRO (CLUE / MRD) Questionnaire			x
Visual Performance			x
Modifications	x	x	
Distance and Near Exit Visual Acuity	x	x	x
Dispensing Criteria	x	x	x
Instructions	x	x	x
Schedule Follow-up	x	x	x
Final Evaluation			x

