**Clinical Study Protocol**  
**Johnson & Johnson Vision Care, Inc.**

Visit 1: Treatment 1 Lens Fitting			
Step	Procedure	Details	[REDACTED]
		
observed:
 
 
• presence of limbal exposure (appearance of clear cornea) in any gaze
 
• presence of edge lift
 
• presence of unacceptable movement (excessive or insufficient) in all three movement categories (primary gaze, upgaze, and push-up).
 
 
NOTE: If lens fit is unacceptable subject will be discontinued from the study. Remove the lenses and complete the Final Evaluation forms.
	[REDACTED]
1.28	Distance and Near Exit Visual Acuity	
Distance and near Snellen visual acuity will be measured for each eye with the study contact lenses in place. For near measures use the ETDRS 2000 Series Chart 1 or 2. The acuity will be recorded to the nearest letter OD, OS and OU.
 
NOTE: The distance visual acuity must be at least 20/30 OU for the lenses to be dispensed.
	[REDACTED]
1.29	Dispensing Criteria	
The following criteria must be met for lenses to be dispensed and if all are not met the subject will be discontinued.
 
 
• Distance Snellen acuity equal to or better than 20/30 OU
 
• Subject must indicate that the vision is acceptable.
 
• Subject must indicate that the comfort of the lenses is acceptable.
 
• Lenses must have an acceptable general lens fit.
 
	
1.30	Patient Instructions	
Instruct the Subject the following:
 
 
• The lenses will be worn on a daily wear basis.
 
• Only enough lenses will be dispensed to the subject to wear for the required number of days until their follow-up
 
	

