### 8.2. Withdrawal/Discontinuation from the Study

A subject will be withdrawn from the study for any of the following reasons:

- Subject withdrawal of consent.
- Subject not compliant to protocol
- Subject lost to follow-up.
- Subject no longer meets eligibility criteria (e.g. the subject becomes pregnant).
- Subject develops significant or serious adverse events necessitating discontinuation of study lens wear
- Subjects who have experienced a Corneal Infiltrative Event (CIE).
- Investigator's clinical judgment regarding the subject safety reasons (that it is in the best interest of the subject to stop treatment).
- Subject not compliant with study lens wear schedule
- Subject not successfully dispensed due to lack of efficacy and safety including poor vision, poor comfort or unacceptable fit.

For discontinued subjects, the Investigator will:

- Complete the current visit (scheduled or unscheduled).
- Complete the Final Evaluation, indicating the reason that the subject was discontinued from the study.
- Record the spherocylindrical refraction with best corrected distance visual acuity.
- Collect used test article(s) (worn or brought to the visit) from the subject and discard them, unless otherwise stated in section 7.2.
- Collect all unused test article(s) from the subject.
- Make arrangements for subject care, if needed, due to their study participation

Additional subjects will be enrolled if a subject discontinues from the study prematurely.

In cases where a subject is lost to follow-up, every possible effort must be made to contact the subject and determine the reason for discontinuation/withdrawal. The measures taken to follow up must be documented including two written attempts and a certified letter (or equivalent) as the final attempt.

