### **Primary Efficacy Analyses:**

All primary efficacy analyses will be conducted on the intent-to-treat population.

Threshold utilized in hypothesis testing related to CLUE vision scores were based on a meta-analysis of CLUE vision scores for the Market leader for multifocal lenses, Air Optix.

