# Clinical Study Protocol

## Johnson & Johnson Vision Care, Inc.

### 14.6. Secondary Analysis

All secondary analyses will be conducted on the Intent-to-Treat population. Threshold utilized in hypothesis testing related to CLUE vision, comfort and handling scores were based on a meta-analysis of CLUE vision, comfort and handling scores for the Market leader for multifocal lenses, Air Optix.

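### The set for every efficacy and secondary test is defined by randomization in a trial that has none, and a few fitted-but-discontinued subjects can decide the fit-success result

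*Combined protocol and SAP*

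**What the plan says.** Section 14.3 defines the Intent-to-Treat population as "All randomized subjects regardless of actual treatment and subsequent withdrawal from study or deviation from protocol", with at least one observation recorded; it does not say an observation of what. Section 5.1 says "Due to the nature of the design no randomization is required". Section 14.5 states "All primary efficacy analyses will be conducted on the intent-to-treat population", and section 14.6 states "All secondary analyses will be conducted on the Intent-to-Treat population". The Safety Population in section 14.3 is "All subjects who were administered any test article excluding subjects who drop out prior to administering any test article", but only the primary safety tests use it.

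In Table 3, the "Follow-up PRO (CLUE / MRD) Questionnaire" and the logMAR visual performance measurement appear at Visit 3 only. Steps 1.29 and 2.15 list four dispensing criteria (distance acuity, acceptable vision, acceptable comfort, acceptable fit) and say "The following criteria must be met for lenses to be dispensed and if all are not met the subject will be discontinued". Section 8.2 gives as a withdrawal reason "Subject not successfully dispensed due to lack of efficacy and safety including poor vision, poor comfort or unacceptable fit", and has discontinued subjects replaced by further enrolment.

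Section 14.9 does not impute missing values in the main analysis. It plans a multiple-imputation sensitivity analysis (parametric regression, at least 50 imputations) if dropout exceeds 10%. Section 14.2 codes fit success as 1 when optimization is achieved in four lenses or fewer and 0 otherwise. Section 14.1 leaves further detail to a stand-alone SAP that is not among these documents.

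**The concern.** The named set has no members if taken literally, and the repair is not unique. Enrolled subjects could include screen failures, because the 120 in section 14.2 allows for screen failures and dropout together. Dispensed subjects would leave out those fitted at Visit 1 who did not meet the dispensing criteria. Fitted subjects would match the Safety Population.

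The choice matters because the protocol itself ties discontinuation to vision, comfort, acuity and fit, and there is no control arm to offset selective loss against a fixed threshold. If discontinued subjects count as fit-success failures, the estimated rate falls; if they are outside the set or treated as missing, it does not. Sections 2.3 and 14.2 imply that they count as failures, but no passage says so for a subject discontinued before optimization. Left open, the denominator could be settled after the data are seen.

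**Working it through.** **The plan's own figures.** Enrolment of 120 for 100 completers implies an allowance of 20/120 = 16.7%, and 100/(1 − 0.167) = 120. This is circular, since no dropout rate is stated. Table 8 gives 82.1% power for fit success with 92 subjects. Simulation under section 14.2's assumptions (true rate 98%, between-eye correlation 0.70, 99% interval, margin 90%) gives 83.6% with a Jeffreys prior, 79.0% with a uniform prior and 88.4% with the N(0, 1000) logit prior of section 14.5. Section 14.2 names no prior, so 82.1% is not contradicted, but the result does depend on the prior.

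**Interval level.** Section 14.4 tests at 1% per hypothesis, with a 99% credible interval for fit success. Sections 14.5 and 14.6 use 95% intervals. Both levels are shown.

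**CLUE vision.** Completers are set at Table 7 values: myopes n = 60, mean 60.6 (SD 16.84), or 60.9 (16.65) for the secondary test; hyperopes n = 40, mean 57.1 (17.27). Add k lost subjects with mean x and the completers' SD (an assumption):

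- M = (n·m + k·x)/(n + k)
- S² = [(n−1)s² + (k−1)s² + n(m−M)² + k(x−M)²]/(n + k − 1)
- lower limit = M − t·S/√(n + k)

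Extreme case for the co-primary tests: the whole allowance of 20 lost (12 myopes, 8 hyperopes), all averaging 0.

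- Myopes: M = 60 × 60.6/72 = 50.5, S = 28.23, 99% half-width 8.81, limit 41.69 against 41. At 95% the limit is 43.87.
- Hyperopes: M = 40 × 57.1/48 = 47.58, S = 27.47, 99% half-width 10.64, limit 36.94 against 36. At 95% the limit is 39.61.

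Both pass at either level.

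For the secondary thresholds (46 and 41) with 12/8 lost averaging 10, the limits are 44.54/39.71 at 99% (fail) and 46.48/42.10 at 95% (pass). The tipping averages are 15.8/14.8 at 99% and 7.9/5.6 at 95%. With 6/4 lost, all at 0, the limits are 47.47/42.23 at 99% (pass).

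**logMAR.** The method is the same, with 100 completers and 20 lost. The result fails only if the lost subjects average worse than 0.30 (distance), 0.71 (intermediate) or 0.36 (near) at 99%, or 0.34, 0.79 and 0.41 at 95%.

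**Fit success.** The lower bound is the 0.5% or 2.5% quantile of Beta(s + a, f + a), where s is successes and f is failures. Jeffreys is a = 0.5, uniform is a = 1, and a = 0 approximates the flat logit prior of section 14.5. Subjects are treated as independent. The pass rule is a lower bound above 0.90, as in section 14.2; section 14.6 prints the upper bound instead. Each cell gives the last pass and the first fail as discontinued subjects are added as failures.

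| Prior, level | From 100/100 | From 98/100 |
|---|---|---|
| Jeffreys, 99% | 100/103: 0.905; 100/104: 0.891 | 98/101: 0.903; 98/102: 0.889 |
| Uniform, 99% | 100/102: 0.913; 100/103: 0.898 | 98/100: 0.911; 98/101: 0.897 |
| Flat logit, 99% | 100/103: 0.912; 100/104: 0.897 | 98/101: 0.911; 98/102: 0.896 |
| Jeffreys, 95% | 100/104: 0.911; 100/105: 0.899 | 98/102: 0.909; 98/103: 0.897 |
| Uniform, 95% | 100/104: 0.905; 100/105: 0.893 | 98/102: 0.904; 98/103: 0.891 |
| Flat logit, 95% | 100/105: 0.904; 100/106: 0.892 | 98/103: 0.903; 98/104: 0.890 |

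The number that reverses the result is therefore 3 to 6 from 100/100 and 1 to 4 from 98/100. The largest case is 6/106 = 5.7% dropout. With 100 completers, passing the 10% trigger takes 12 dropouts (11/111 = 9.9%, 12/112 = 10.7%); out of 120 it takes 13.

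**The case against.** **The definition is a slip with an obvious reading.** All subjects are assigned one lens, and the definition keeps them regardless of withdrawal. For CLUE and logMAR this stands: only subjects with Visit 3 values contribute, so changing the set alters no main result. It does not stand for fit success, where a subject can be classed as a failure without reaching Visit 3.

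**The target is declared.** Section 2.3 words the CLUE and logMAR hypotheses for the optimized lenses after about a week of wear. That is correct, and the means are legitimate on those terms.

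**The failure coding is nearly explicit.** This is also fair: sections 2.3 and 14.2 point to coding these subjects as 0. Fit success is a secondary test, reached only after all co-primaries pass.

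**The stand-alone SAP may settle this.** It may; it cannot be checked here.

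A reader might also infer more than the documents support:

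- *That no analysis covers the discontinued subjects.* Section 14.9 plans multiple imputation above 10% dropout, and fit failures are counted at all visits in a co-primary safety test on the Safety Population.
- *That imputation cannot help when loss follows the outcome.* The dispensing criteria are assessed at Visits 1 and 2, so the loss could be at random given those variables if they were in the model. The gap is that no predictors are named, the trigger may not be met, and there is no not-at-random scenario.
- *That 12% to 15% loss should be expected.* Table 6 shows safety-to-per-protocol losses of 51/413 (12.3%), and 23/153 (15.0%) in the two efficacy-planning studies. These include deviation exclusions and come from multi-period designs, so they carry over poorly to a single-arm study of about ten days.

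**Conclusion.** The concern holds, and its weight falls on fit success. The governing set cannot be applied as written, and how 1 to 6 fitted-but-discontinued subjects are counted can reverse that test while dropout is still below the level that triggers any sensitivity analysis. Table 7's 100% fit success gives no reassurance, because it is a per-protocol rate.

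The tempting stronger conclusion, that the co-primary efficacy results are in doubt, is not supported. At Table 7 values co-primary CLUE passes with all 20 lost subjects at zero, and logMAR needs implausibly poor averages to fail. Secondary CLUE vision fails only in an extreme case. The documents give no count of discontinuations by reason, so the actual bias is unknown.

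The fit-success counts assume independent subjects, the three priors shown and a lower-bound rule. Sections 2.3 and 14.6 take the subject as the unit, while section 14.2 uses a between-eye correlation. The 99%/95% conflict accounts for part of the spread.

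**What to change.** 1. Reconcile the 99% and 95% intervals first, since the pass rules depend on them.
2. Define the efficacy and secondary set as all subjects fitted with a test lens, matching the Safety Population.
3. State that subjects discontinued for vision, comfort, acuity or fit before obtaining an optimum pair stay in the fit-success denominator as failures. Handle unrelated exits (for example pregnancy or COVID-19) separately, with a sensitivity analysis that counts them as failures.
4. For CLUE and logMAR, put the recorded Visit 1 and 2 acuity, vision, comfort and fit variables in the imputation model. Add a tipping-point analysis that runs whatever the dropout rate.
5. Report discontinuations by reason, already recorded at the Final Evaluation, beside the means, and label the means as applying to wearers of the optimized lenses.

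The cost is SAP wording and one extra analysis, with no new data or visits. The downside is a possibly lower fit-success rate, which could change that secondary result. The change should be made before database lock.
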